1.6 Risk-benefit Summary

MEDI-551 may offer a benefit to patients with CD19-expressing hematologic malignancies who have failed standard therapies. Nonclinical and clinical data support the antitumor activity of MEDI-551 in a variety of B-cell malignancies. Specifically, MEDI-551 showed response rates of 19% in CLL, 29% in FL, and 23% in DLBCL subjects who had received a median of 5 prior lines of therapy. Currently, infusion reactions are an identified risk of MEDI-551 treatment. Potential risks, based on the mechanism of action of MEDI-551, and data from nonclinical safety and pharmacology studies and published literature on relevant or similar therapies (primarily rituximab) include the following: acute hypersensitivity reactions, tumor lysis syndrome, IM-related reactions, immunosuppression with increased risk of infection, and adverse reproductive effects. There are, however, no clinical or nonclinical data to suggest that the toxicity profile of MEDI-551 will compare unfavorably to rituximab. Clinical data suggest the toxicities observed are consistent with the toxicity profile of other MABs and B-cell-depleting agents.

The proposed Phase 1/2 trial will characterize both the safety and antitumor activity of MEDI-551 in B-cell malignancies, with the goal of more fully elucidating its risk-benefit profile. The exclusion criteria, safety monitoring, starting dose, dose-escalation scheme, and stopping criteria will minimize the risks for subjects participating in the monotherapy and combination therapy arms of the study.

The combination of rituximab and MEDI-551 has the potential for additive toxicities including acute hypersensitivity reactions, tumor lysis syndrome, IM-related reactions, immunosuppression with increased risk of infection, and potential adverse reproductive effects. The dosing schema for MEDI-551 and rituximab has been altered to minimize the risk of infusion-related AEs by separating MEDI-551 and rituximab dose administration on Day 1 of Cycle 1. Additional changes to the administration of MEDI-551, including change in the infusion rate and additional steroid premedication together with administration of an

anti-pyretic and H2-blocker, have been mandated to further minimize this risk. To further reduce the risk of additive toxicities, the dose-escalation schema in the combination arm (Arm C) starts with a 33.3% lower dose of MEDI-551 (ie, 8 mg/kg) than the maximum dose demonstrated as safe (ie, 12 mg/kg) in the single-agent treatment of subjects with B-cell malignancies. Finally, DLT criteria and dose-modification schemas have been adjusted to address the potential for increased hematologic and non-hematologic toxicities. Additional follow-up has been implemented to further ensure the safety of subjects (Section 6.3).

Based on the observed pharmacologic activity and mechanism of action of MEDI-551, as well as the considerable clinical experience with marketed products such as rituximab, which has a similar mechanism of action, the risk-benefit profile is considered acceptable for the single-agent arms (Arms A, B, and D) of the clinical study. In addition, with the safety provisions listed above and the knowledge that B-cell-targeted MABs have been successfully and safely combined to treat this population, the risk-benefit profile is considered acceptable for the dual-antibody arm (Arm C) of this study.

2 STUDY OBJECTIVES

2.1 Primary Objectives

The primary objectives of this study are listed by study arm.

Arm A

1. To determine the MTD or OBD of MEDI-551 in subjects with relapsed or refractory advanced B-cell malignancies (CLL, including SLL, DLBCL, and FL)
2. To determine the preliminary safety profile of MEDI-551

Arm B

Dose escalation

1. To determine the MTD or highest protocol-defined dose of MEDI-551 in the absence of exceeding the MTD in subjects with relapsed or rituximab-refractory CLL (defined as those with less than a PR or progression within 6 months after completing therapy with rituximab)

Dose expansion

1. To evaluate further the safety and tolerability of MEDI-551 at the dose selected in the dose-escalation phase in subjects with relapsed or rituximab-refractory CLL

2. To evaluate the clinical activity of MEDI-551 at the dose selected in the dose-escalation phase in subjects with relapsed or rituximab-refractory CLL

Arm C

Dose escalation

1. To determine the safety and tolerability of MEDI-551 in combination with rituximab at the MTD or the highest protocol-defined dose in the absence of exceeding the MTD in subjects with aggressive lymphomas

Dose expansion

1. To evaluate further the safety and tolerability of MEDI-551 at the dose selected in the dose-escalation phase in subjects with aggressive lymphomas
2. To evaluate the clinical activity of MEDI-551 at the dose selected in the dose-escalation phase in combination with rituximab in relapsed and rituximab-refractory population (defined as those with less than a PR or progression within 6 months after completing therapy with rituximab)

Arm D

1. To evaluate the clinical activity of MEDI-551 in subjects with any anti-CD20-refractory aggressive lymphomas (defined as any subject with less than a PR to any prior anti-CD20-based therapy or progression within 6 months after completing therapy with any anti-CD20-based regimen, including maintenance rituximab)

2.2 Secondary Objectives

The secondary objectives of this study are listed by study arm.

Arm A

1. To determine the preliminary efficacy profile of MEDI-551 in subjects with advanced B-cell malignancies (CLL [including SLL], DLBCL, and FL)
2. To determine the PK of MEDI-551 in subjects with advanced B-cell malignancies
3. To determine the effect of treatment with MEDI-551 on circulating lymphocyte populations and Ig levels, including time to recovery after treatment
4. To determine the IM of MEDI-551 in subjects with advanced B-cell malignancies

Arm B

1. To evaluate the PK and IM of MEDI-551 at doses studied in subjects with relapsed or rituximab-refractory CLL
2. To evaluate the effect of therapy on the B-lymphocyte level in peripheral blood, including time to recovery of B-lymphocyte level

Arm C

1. To evaluate the PK and IM of MEDI-551 when administered in combination with rituximab in subjects with aggressive lymphomas
2. To evaluate the effect of therapy on the B-lymphocyte level in peripheral blood, including time to recovery of B-lymphocyte level

Arm D

1. To determine the safety and tolerability of MEDI-551 in subjects with any anti-CD20-refractory aggressive lymphomas
2. To evaluate the PK and IM of MEDI-551
3. To evaluate the effect of therapy on the B-lymphocyte level in peripheral blood, including time to recovery of B-lymphocyte level

2.3 Exploratory Objectives

The exploratory objectives of this study are listed by study arm.

Arm A

1. [REDACTED]

Arm B

1. [REDACTED]
2. [REDACTED]
3. [REDACTED]

Arm C

1. [REDACTED]
2. [REDACTED]

Arm D

1. [REDACTED]
2. [REDACTED]

3 STUDY DESIGN

3.1 Overview of Study Design

This is a Phase 1/2, multicenter, international, open-label, dose-escalation and expanded cohort study to evaluate the safety, tolerability, and potential antitumor activity of MEDI-551 as single agent or in combination with rituximab in adult subjects with advanced B-cell malignancies. The study design of Arm A comprised a dose-escalation phase followed by a dose-expansion phase in subjects with advanced B-cell malignancies receiving single-agent MEDI-551.

As of Version 10.0 of the protocol, the study design also includes dose escalation and expansion in subjects with CLL receiving single-agent MEDI-551 (Arm B), and dose escalation and expansion in subjects with aggressive lymphoma receiving MEDI-551 combined with rituximab (Arm C). As of Version 11.0 of the protocol, the study design also includes subjects with any anti-CD20-refractory aggressive lymphoma receiving single-agent MEDI-551 (Arm D).

This study included participants from 21 investigational sites in the United States (US), Canada, and European Union (EU).

Enrollment in the study was closed as of 30Sep2015. As of 19Jan2017, 9 subjects remain on treatment; all have completed at least 1 year of treatment. All subjects who are currently receiving MEDI-551 treatment may continue to receive MEDI-551 until disease progression, unacceptable toxicity, CR, withdrawal of consent, or another reason to discontinue therapy intervenes. Subjects who achieve CR may receive 2 additional cycles at the same dose prior to EOT Visit. A simplified schedule of evaluations focused on safety will be used. Safety follow-up assessments will be conducted at the EOT_Visit (defined as the last day of the last

cycle of investigational product administration) as well as at the 90-Day Post Last Dose Visit (defined as 90 days after the last dose of study medication), which will serve as the End of Study Visit. Long-term follow-up for PFS and OS will not be performed following implementation of Version 13.0.

Arm A

Enrollment in the dose-escalation and dose-expansion phases of Arm A is complete. Protocol Version 4.0 was amended to make the study population for dose-escalation inclusive of subjects with FL, MM, CLL, or DLBCL. Dose escalation in Arm A began in subjects with FL or MM per protocol Versions 1.0 through 4.0. Under these versions of the protocol, subjects were enrolled into the first 2 cohorts. Starting with Version 5.0 of the protocol, enrollment in dose-escalation Cohorts 3 and higher was open to subjects with the following advanced B-cell malignancies: FL, MM, CLL, or DLBCL. Subjects in Cohorts 1 and 2 continued to follow the protocol Version 4.0 dose schedule of 0.5 mg/kg (Cohort 1) or 1 mg/kg (Cohort 2) MEDI-551 administered IV once every week in 4-week cycles. Subjects enrolled in Cohorts 3 and higher received 2, 4, 8, or 12 mg/kg MEDI-551 (Cohorts 3 to 6, respectively) IV once per week on Days 1 and 8 of Cycle 1 (loading doses) and then once every 28 days at the start of each subsequent cycle. Rules for dose escalation are provided in Section 4.5.5. As per Cohorts 1 and 2, dosing in Cohorts 3 and higher followed a standard 3+3 dose-escalation scheme. No intrasubject dose escalation was allowed. The dose cohorts for the dose-escalation phase in Arm A are shown in [Figure 3.1-1](#).

[figure not shown]

Figure 3.1-1 Flow Diagram for Dose Escalation in Arm A

CLL = chronic lymphocytic leukemia; DLBCL = diffuse large B-cell lymphoma; FL = follicular lymphoma; MM = multiple myeloma.

Note: Subjects in Cohorts 1 and 2 were treated as per Version 4.0 of the protocol. Subjects in Cohorts 3 and beyond were as per Version 5.0 and subsequent versions of the protocol.

Subjects continued to receive MEDI-551 until disease progression, toxicity, or another reason to discontinue therapy intervened. All subjects (US and non-US) who achieved a CR could have received an additional 2 cycles of MEDI-551 at the same dose. Rules for dose escalation are described in Section 4.5.5. A total of approximately 18 to 36 evaluable subjects were required for the dose-escalation phase; 26 were enrolled. Subjects were considered evaluable if they received at least one full cycle (4 doses for Cohorts 1 and 2; 2 doses for Cohorts 3 to 6) of MEDI-551 and completed the safety follow-up through the

DLT evaluation period as defined in Section 4.5.6, or experienced any DLT. Non-evaluable subjects were replaced in the same dose cohort. Dose escalation continued until the MTD (if ≤ 12 mg/kg), the 12-mg/kg maximum dose, or a lower dose (the OBD) as determined by a combination of safety, PK, pharmacodynamic, and response data was reached.

Following determination of the MTD or OBD, approximately 80 subjects total, 20 subjects each with FL, MM, CLL, or DLBCL, were to be enrolled in the dose-expansion phase of Arm A to determine the preliminary efficacy profile of MEDI-551 in the treatment of advanced B-cell malignancies. As of Version 8.0 of the protocol, enrollment of MM subjects in the expansion phase was discontinued based on data from this study and recent nonclinical studies suggesting a lack of activity in the advanced/refractory MM setting. Twenty subjects each with FL, CLL (including SLL), or DLBCL were enrolled in the dose-expansion phase for a total of approximately 60 evaluable subjects. A total of 69 subjects (24 CLL, 21 DLBCL, 23 FL, and 1 MM) were enrolled.

Subjects in the dose-expansion phase of Arm A were treated on Days 1 and 8 of Cycle 1 (loading doses) and then once every 28 days at the start of each subsequent cycle at the MTD, maximum dose of 12 mg/kg, or OBD as determined in the dose-escalation phase. A preplanned interim safety analysis, as defined in the statistical analysis plan, was undertaken when the maximum dose was reached to examine treatment effects on key safety endpoints. As of Version 7.0 of the protocol, the dose-escalation phase of Arm A had been completed. No MTD or OBD was identified during the dose-escalation phase; therefore the expansion phase of Arm A proceeded using the previously selected maximum dose of 12 mg/kg. The preplanned interim safety analysis was conducted at the completion of the dose-escalation phase. No significant safety findings were noted and no changes were made to the protocol as a result of these findings.

If evaluation of available safety, PK, pharmacodynamic, and efficacy data suggest that increased safety and/or efficacy is possible with a longer dosing interval, an extended interval may be evaluated. Subjects who achieved a CR may receive an additional 2 cycles of MEDI-551 at the same dose. Once Version 13.0 is in effect, re-treatment will not be available for subjects who achieve a CR and subsequently relapse while off treatment. Prior to Version 13.0, the US FDA was to be consulted concerning the possibility of additional treatment with MEDI-551 for subjects within the US, and US subjects enrolled in Arm A could have been retreated at the 12-mg/kg dose at the discretion of the investigator and after discussion with the sponsor. Non-US subjects in Arm A were not to be retreated with MEDI-551 on subsequent relapse.

[figure not shown]
Arm B

Enrollment in Arm B is complete. Based on evaluation of the PK data in CLL subjects (n = 26) from Arm A, there appeared to be lack of full exposure and numerically lower response rate compared to non-CLL subjects using the current monthly dosing regimen at the highest dose evaluated (ie, 12 mg/kg). This arm of the study evaluated further dose escalation in CLL subjects utilizing a new schema, designed to saturate the potential B-cell sink, achieve full exposure, and maximize clinical activity, by employing weekly dosing of MEDI-551 for 4 weeks during Cycle 1 and then monthly dosing on Day 1 of each subsequent 28-day cycle to determine the MTD or the highest protocol-defined dose in the absence of exceeding the MTD, which would be evaluated in a dose-expansion phase. To further minimize infusion-related reactions at higher dose levels, for the 24 and 48 mg/kg dose levels of MEDI-551, the initial weekly doses were to be administered over 2 days on Day 1 and Day 2 in Cycle 1. Subsequent doses at the 24 and 48 mg/kg dose levels were to be administered in an identical fashion to lower dose levels (ie, weekly on Days 8, 15, and 22 in Cycle 1 and then on Day 1 of each 28-day cycle in Cycle 2 and beyond). Note that the 48 mg/kg cohort was not enrolled. A flow diagram for Arm B is provided in [Figure 3.1-2](#).

Using a standard 3+3 design, 3 to 6 subjects with CLL were to be enrolled per cohort, starting at a dose of 6 mg/kg and escalating to 3 additional dose levels (12, 24, and 48 mg/kg) in the dose-escalation phase of this arm. Treatment may continue until the subject experiences unacceptable toxicity, disease progression, achieves CR (2 additional cycles at the same dose may be given prior to EOT) or withdraws consent. If 0 of 3 or ≤ 1 of 6 subjects treated at the previous dose level experienced a DLT, dose escalation could continue. The MTD was defined as the dose at which no more than 1 of 6 subjects experienced a DLT during Cycle 1. No intrasubject dose escalation was allowed. Subjects were considered evaluable for a DLT if they completed their first cycle of therapy or discontinued therapy during Cycle 1 due to a DLT. Nonevaluable subjects were to be replaced in the same dose cohort. A total of up to 24 subjects were to be enrolled in the dose-escalation portion of this arm. Dose escalation was permitted after all investigators reviewed the available data after a data review meeting and unanimously agreed to proceed with enrollment into the next cohort. The outcome from this meeting was documented in writing and shared with all participating sites.

Once an MTD was identified or the maximum planned dose not exceeding the MTD was reached, additional CLL subjects were to be enrolled at the selected dose in the dose-expansion phase to ensure a total of 26 efficacy evaluable subjects were available for analysis after completing one post-treatment disease evaluation. The dose-expansion phase

included subjects treated at the MTD or maximum planned dose enrolled in the dose-escalation phase of this arm. Treatment may continue until the subject experiences unacceptable toxicity, disease progression, withdraws consent, or achieves CR (2 additional cycles at the same dose may be given prior to EOT).

^a MEDI-551 will be initiated at a dose of 6 mg/kg. Subsequent cohorts will evaluate doses of 12, 24, and 48 mg/kg.
^b MTD or maximum planned dose not exceeding the MTD identified in the dose-escalation phase.

Figure 3.1-2 Flow Diagram for Dose Escalation and Expansion in Arm B

MTD = maximum tolerated dose.

* Note: For the 24 and 48 mg/kg cohorts, the initial weekly doses were administered over 2 days on Day 1 and Day 2 in Cycle 1. Subsequent doses for the 24 and 48 mg/kg cohorts were to be administered weekly on Days 8, 15, and 22 in Cycle 1 and then on Day 1 of each 28-day cycle in Cycle 2 and beyond. Note that the 48 mg/kg cohort was not enrolled.

Arm C

Enrollment in Arm C is complete. Given the high unmet medical need in patients with multiply relapsed aggressive lymphoma, the synergistic activity observed in preclinical studies with MEDI-551 and rituximab, as well as the promising clinical activity seen with other dual MAb combinations in patients with B-cell malignancies, this arm of the study evaluated the safety and efficacy of MEDI-551 in combination with rituximab in subjects with aggressive lymphoma (relapsed or refractory DLBCL, Grade 3b FL, FL transforming to

DLBCL and MCL) in dose-escalation and dose-expansion cohorts. A flow diagram for Arm C is provided in [Figure 3.1-3](#).

Using a standard 3+3 design, 3 to 6 subjects with aggressive NHL were enrolled per cohort in the dose-escalation portion of this arm, starting at a MEDI-551 dose of 8 mg/kg and escalating to 12 mg/kg. Subjects in this arm received weekly rituximab for 8 weeks beginning on Day 1 of Cycle 1 along with MEDI-551 8 mg/kg on Days 2 and 8 of Cycle 1, and on Day 1 of Cycle 2 and beyond in 28-day cycles. Dose escalation continued to 12 mg/kg as 0 of 3 or ≤ 1 of 6 subjects treated at the lower dose experienced a DLT. The MTD was defined as the dose at which no more than 1 of 6 subjects experienced a DLT. No intrasubject dose escalation was allowed. Subjects were considered evaluable for a DLT if they completed their first cycle of therapy or discontinued therapy during Cycle 1 due to a DLT. Nonevaluable subjects were to be replaced in the same dose cohort. A total of up to 12 subjects were to be enrolled in the dose-escalation portion of this arm of the study. Dose escalation was permitted after all investigators reviewed the available data during a data review meeting and unanimously agreed to proceed with enrollment into the next cohort. The outcome from this meeting was documented in writing and shared with all participating sites.

Once an MTD was identified or the maximum planned dose not exceeding the MTD was reached, additional subjects were to be enrolled and treated at the selected dose of MEDI-551 in combination with rituximab in the dose-expansion portion of this arm to ensure a total sample size of 26 efficacy evaluable subjects were available for analysis after completing one post-treatment disease evaluation. The 26 subjects were to include subjects treated at the selected dose during the dose-escalation portion of this arm. Treatment may continue until the subject experiences unacceptable toxicity, disease progression, withdraws consent, or achieves a CR (2 additional cycles of MEDI-551 at the same dose may be administered before EOT). A total of 19 subjects were enrolled in Arm C.

Subjects in Arm C were stratified based on their responsiveness to any prior anti-CD20-based therapy with the option of ensuring a minimum number of 7 subjects who are refractory to any prior anti-CD20-based therapy are enrolled if clinical data from Arm D or emerging preclinical data suggest that the combination of anti-CD20 and anti-CD19 therapies improve response in this subpopulation.

[figure not shown]

Figure 3.1-3 Flow Diagram for Dose Escalation and Expansion in Arm C

MTD = maximum tolerated dose.

Arm D

Enrollment in Arm D is complete. Given the high unmet medical need in patients with refractory aggressive lymphoma and in light of preservation of CD19 expression on the surface of these malignant cells, MEDI-551 may represent a salvage therapy option for anti-CD20-refractory patients. Evidence of clinical activity and safety of MEDI-551 in an unselected patient population (Arm A) supported investigating MEDI-551 in the anti-CD20-refractory population. Arm D evaluated the clinical activity of MEDI-551 in subjects with any anti-CD20-refractory aggressive lymphoma (refractory DLBCL, Grade 3b FL, FL transforming to DLBCL, and MCL). A flow diagram for Arm D is provided in [Figure 3.1-4](#).

Since the safety and tolerability of the 12-mg/kg dose of MEDI-551 has been verified in Arm A, approximately 26 subjects with any anti-CD20-refractory disease were to be enrolled and treated with single-agent MEDI-551 at the dose and schedule used in the expansion cohort of Arm A (ie, 12 mg/kg of MEDI-551 on Days 1 and 8 of Cycle 1, and on Day 1 of Cycle 2 and beyond in 28-day cycles). A total of 16 subjects were enrolled in Arm D. Treatment may continue until the subject experiences unacceptable toxicity, disease

progression, withdraws consent, or achieves a CR (2 additional cycles of MEDI-551 at the same dose may be administered before EOT).

[figure not shown]

Figure 3.1-4 Flow Diagram for Treatment in Arm D

The endpoints to be measured in this study are described in Section 7.3.

3.2 **Estimated Study Duration**

The duration of investigational product treatment will be determined by disease response and safety. Safety follow-up assessments will be conducted through approximately 90 days after the last dose of investigational product, which is equivalent to approximately 60 days post-EOT Visit. The estimated study duration is approximately 8 to 10 years from the time the first subject is enrolled in the study. Study completion is defined as the date of the last protocol-specified visit for the last subject in the study.

4 **STUDY PROCEDURES**

4.1 **Subject Participation and Identification**

Study participation begins once written informed consent is obtained (see Section 10.3 for details). Once informed consent is obtained, a subject identification (SID) number will be assigned by a central system (eg, an interactive voice response system [IVRS]), and the screening evaluations may begin to assess study eligibility (inclusion/exclusion) criteria. The

SID number will be used to identify the subject during the screening process and throughout study participation, if applicable.

A master log will be maintained of all consented subjects and will document all screening failures (ie, subjects who are consented but do not meet study eligibility criteria).

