4.7 Subject Status

Subject Completion

An individual subject will be considered to have completed the study if the subject was followed for survival until death or end of the study, regardless of the number of doses of investigational product that was received. Once Version 13.0 is in effect, all subjects who have completed treatment and the 90-Day Post Last Dose Visit for safety follow-up will be considered to have completed the study.

Until Version 13.0, is in effect, subjects will be considered not to have completed the study if one of the following conditions applies:

- **Withdrawal of consent:** If consent for follow-up is withdrawn, the subject will not receive any further investigational product or further study observation. Note that the subject may need to undergo additional tests or tapering of treatment to withdraw safely.
- **Lost to follow-up:** Subjects will be considered lost-to-follow-up only if no contact has been established by the time the study is completed such that there is insufficient information to determine the subject's status on the last day of the study.

Note: Subjects refusing to return to the site or to continue participation in the study should be documented as "withdrawal of consent" rather than "lost to follow-up." Investigators should document attempts to re-establish contact with missing subjects throughout the study period. If contact with a missing subject is re-established, the subject should not be considered lost-to-follow-up and any evaluations should resume according to the protocol at the point that they would be if no evaluations had been skipped.

Permanent Discontinuation of Investigational Product

Subjects who do not receive all protocol-specified doses of the investigational product, regardless of the reason (withdrawal of consent, due to an AE, other), will be identified as having permanently discontinued treatment.

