13. Achievement of a CR and a maximum of 2 additional cycles after CR. For the purposes of discontinuation of drug, CR shall be defined as the time of hematological and radiological CR without necessity of BM confirmation.

Subjects who are permanently discontinued from investigational product will be followed for safety for approximately 90 days post last dose. In addition, until Version 13.0, subjects were to be followed for disease evaluation every 3 months after the 90-Day Post Last Dose Visit until disease progression, death, initiation of alternative therapy, withdrawal of consent, or end of study. Upon disease progression, subjects were to be followed only for survival every 3 months until death, withdrawal of consent, or end of study.

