- **Progression-free survival:** Progression-free survival will be measured from start of MEDI-551 administration until the first documentation of PD/relapse or death, whichever occurs first. Progression-free survival will be censored on the date of last disease assessment for subjects who have no documented PD/relapse or death prior to data cutoff, dropout, or the initiation of alternative anticancer therapy.
- **Overall survival:** Overall survival will be determined as the time from the start of MEDI-551 administration until death. For subjects who are alive at the end of study or lost to follow-up, OS will be censored on the last date when subjects are known to be alive.

The analysis methods will differ by the types of endpoints. For categorical endpoints, proportions will be summarized, 80% and 95% confidence intervals will be calculated using the Clopper-Pearson exact method. For time-to-event endpoints, Kaplan-Meier method will be used to describe the endpoints graphically and to estimate the median or the event rates at time of interest.

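### Up to 9 subjects still on treatment at Version 13.0 are followed for survival only until about 90 days after stopping, and with no OS data cutoff stated the late OS curve leans upward

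*Protocol*

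**What the plan says.** Before Version 13.0, survival follow-up continued after treatment failure. Section 6.4.1 records: "Upon disease progression, subjects were to be followed only for survival every 3 months until death, withdrawal of consent, or end of study".

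Version 13.0 ends this. Section 3.1: "Long-term follow-up for PFS and OS will not be performed following implementation of Version 13.0". What remains is the safety visit (Section 6.4.1): "Subjects who are permanently discontinued from investigational product will be followed for safety for approximately 90 days post last dose". Section 4.7 makes that visit the end of participation: "Once Version 13.0 is in effect, all subjects who have completed treatment and the 90-Day Post Last Dose Visit for safety follow-up" count as having completed the study.

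Some subjects stay under observation after the change. Section 3.1: "As of 19Jan2017, 9 subjects remain on treatment; all have completed at least 1 year of treatment". They may continue until progression, toxicity, CR, withdrawal or another reason.

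OS remains an endpoint: among the primary clinical activity measures in Arms B, C and D (Section 7.3.1) and secondary in Arm A (Section 7.3.2). For time-to-event endpoints, Section 7.4.3 says the "Kaplan-Meier method will be used to describe the endpoints graphically and to estimate the median or the event rates at time of interest". Where no death is known by the time the study ends or contact is lost, the rule is: "OS will be censored on the last date when subjects are known to be alive". The PFS rule in the same section refers to subjects with "no documented PD/relapse or death prior to data cutoff, dropout, or the initiation of alternative anticancer therapy". The duration rules also name a data cutoff; the OS rule does not.

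**The concern.** Kaplan-Meier treats censored subjects as having the same future risk as those who stay under observation. For subjects off treatment when Version 13.0 takes effect, that is reasonable: the exit date is set by the calendar. For subjects still on treatment it is doubtful. They stay in the risk set while treatment goes on and leave about 90 days after it stops. If a subject stops for progression, a death later than that is not seen.

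After Version 13.0 the person-time being added is therefore mostly on-treatment time, and deaths after the 90-day visit drop out. Estimated late mortality is too low and the curve too high. At stake is how the OS tail is read, especially in Arms C and D, where follow-up is shorter and few subjects remain at risk.

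**Working it through.** The protocol gives no OS estimate, event count or power figure, so there is nothing of its own to reproduce. The check has three parts.

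**1. How many subjects.** Enrolled: Arm A 26 + 69 = 95, Arm B 7, Arm C 19, Arm D 16 (Sections 3.1, 7.5 and 15). Total 95 + 7 + 19 + 16 = 137. On treatment at 19Jan2017: 9, and 9/137 = 6.6%. The other 128 (93.4%), less deaths and earlier losses, are censored by calendar date.

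**2. Which part of each curve.** Months to the Version 13.0 document date, 01Jun2017 (days / 30.44):

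- Enrollment closed 30Sep2015: 610 days = 20.0 months. Every subject has at least this much potential follow-up, so no arm is affected earlier.
- Version 10.0, 07Oct2013: 1333 days = 43.8 months. Section 15 records that Arm A was fully enrolled by then, so its curve is unaffected before about 44 months. Arms B and C opened with this version, so 43.8 months is their maximum.
- Version 11.0, 21Mar2014: 1168 days = 38.4 months, the maximum for Arm D.

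Beyond 43.8 months (Arms B, C) or 38.4 months (Arm D), the only subjects at risk are those on treatment, or within 90 days of the last dose, at Version 13.0.

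**3. How large.** The estimate is S(t) = ∏(1 − dᵢ/nᵢ). Subjects on treatment at Version 13.0 stay in nᵢ until about 3 months after stopping; their later deaths never enter dᵢ. The protocol gives no survival times, so the size was simulated under stated assumptions, with 400,000 subjects per scenario and exponential times.

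Arm C/D-like inputs: entry spread evenly from 40 to 20 months before Version 13.0; median time on treatment 3 months for 80% of subjects and 20 months for 20% (8.9% still on treatment at 19Jan2017); median survival after stopping 6 or 12 months; study end 36 months after Version 13.0.

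| Survival at month | 12 | 20 | 24 | 36 | 48 |
|---|---|---|---|---|---|
| True, 6-month median | 0.517 | 0.285 | 0.216 | 0.106 | 0.060 |
| Rule as written | 0.517 | 0.285 | 0.219 | 0.132 | 0.114 |
| Common cutoff | 0.517 | 0.285 | 0.216 | 0.106 | 0.086 |
| True, 12-month median | 0.696 | 0.489 | 0.408 | 0.239 | 0.142 |
| Rule as written | 0.696 | 0.489 | 0.410 | 0.268 | 0.241 |
| Common cutoff | 0.696 | 0.489 | 0.408 | 0.239 | 0.201 |

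Differences before rounding, rule as written minus true: 0.0 points at 12 and 20 months, +0.2 at 24, +2.6 and +2.8 at 36, +5.4 and +9.8 at 48. The common cutoff matches the truth at 36 months. At 48 months it is only a flat extension past the last available follow-up (40 months here), which is why estimates there should not be reported.

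A separate simulation with Arm A's longer follow-up gave about +0.2 to +0.6 points at 60 months.

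Sensitivity to the reason for stopping, all arms pooled (entry 82 to 20 months before Version 13.0, 12-month median survival after other stops): +1.7 points at 48 months if no late stop is for CR, and +1.3 if every stop after 12 months is for CR with a 60-month median survival afterwards. The direction did not change.

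**The case against.** The strongest reply is that a cutoff date belongs in the SAP, to which Section 7.1 sends the details of endpoint analyses, and that nothing in the protocol says survival time gathered after Version 13.0 will be analysed. This stands in part: the lean arises only if that time is used, and the SAP, not available to this review, may already exclude it. But Section 7.4.3 fixes the OS censoring rule itself and names a data cutoff for the neighbouring endpoints only. Applied as written, the rule takes in the late follow-up.

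OS also has no hypothesis, power calculation or decision rule; Section 7.5 rests on CR and response rates. That stands, and it limits the importance of the point.

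A reader might infer that OS censoring in general follows treatment failure. It does not: subjects who had left treatment were followed three-monthly, including after progression, and then stopped administratively. Nor do the documents show that the 9 will leave mostly for progression. Treatment also ends for CR, toxicity or withdrawal, and Section 15 reports durable responses in Arm A subjects who stopped in CR. Nor can the 9 be called nearly all of the late risk set in Arm A, because the number of off-treatment subjects alive at Version 13.0 is not given.

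**Conclusion.** The point holds as a limited one. For up to 9 of 137 subjects, leaving survival follow-up is tied to stopping treatment, and the OS rule has no cutoff to keep that follow-up out. The late curve then leans upward, in every scenario tried.

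The size rests on assumed rates: roughly +2 to +3 points at 36 months for Arm C/D-like follow-up, +5 to +10 at 48 months where only on-treatment subjects remain, and under 1 point at 60 months in Arm A in most scenarios. Nothing changes before about 20 months in Arms B to D or about 44 months in Arm A, so medians and rates before those times are safe.

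A reader might restart the clock at Version 13.0 in the on-treatment subjects alone and find a far larger gap. Assuming 20% to 40% progression per year, 2% deaths per year on treatment and 0.3 to 0.7 deaths per year after progression, true 3-year survival is 51% to 79% against a Kaplan-Meier estimate of 79% to 91%. The plan estimates no such curve, so those figures do not measure the error in the planned analysis.

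**What to change.** In Section 7.4.3, and in the SAP if it differs, state one OS data cutoff for all arms: a single calendar date no later than the first site implementation of Version 13.0. A single date is needed because the protocol gives only the document date, and sites may implement on different days.

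Count deaths on or before the cutoff as events. Censor all others at the earlier of the last date known alive and the cutoff. Do not credit every subject as alive to the cutoff: contacts were three-monthly, and that would miss deaths since the last one. List later deaths and follow-up without analysing them, and report no OS estimate beyond the follow-up available at the cutoff.

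This is a short addition to the analysis section, with no new data and no change to visits or treatment. The cost is a little late survival time from about 9 subjects.
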